## **8. Risks**

We believe the risks associated with completing assessments and participating in the intervention are minimal. Potential risks include: temporary daytime fatigue (due to restriction of time in bed), subjective discomfort from answering questionnaires, coercion, and the possibility of a breach of confidentiality. Because the sleep restriction component of CBT-I places individuals with a history of mania at risk for additional manic episodes, the treatment will be modified for these individuals. Participants will not incur financial risk. There are no other known iatrogenic effects of CBT-I or completion of sleep diaries. However, if any emerge, they will be addressed immediately by research and/or clinical staff.

The following safeguards will be implemented to protect participants from risks related to study participation:

*Temporary fatigue.* Participants will be informed as part of the consent process that restricting their time in bed may increase daytime fatigue for the first few weeks of treatment (although this will be temporary, as time in bed will be expanded as sleep efficiency improves). Consistent with standard insomnia treatment procedures, time in bed will never be restricted to less than 5 hours in order to avoid impaired vigilance and significant daytime sleepiness. Participants will also be provided with recommendations on ways to increase alertness and counter daytime fatigue (e.g., staying active, engaging in social activities).

*Discomfort.* Participants will be informed of the types of questions that they will be asked to answer as part of the informed consent process, and they will have the opportunity to skip questionnaire items or discontinue participation in the study at any time without penalty. Referrals will be provided to participants during the consent and throughout the study, in the event that participants report experiencing distress.

*Coercion.* Participants will be provided with modest compensation for their participation in the study (up to \$150 for 3 assessments and 3 complete weeks of daily sleep surveys). We believe these compensation rates are commensurate with the time and effort involved in these tasks, and the amounts are consistent with compensation provided for other clinical studies with Veterans. Participants are free to discontinue at any time and will receive compensation for any and all assessments that they complete.

*Confidentiality.* Study data will be handled only by research staff and will be used strictly for research purposes. All research staff will be trained in responsible research conduct and the handling of private and confidential information. Identifying information will not be recorded in computerized or paper-and-pencil assessments; rather, assessment instruments and related study data will be identified and tracked using a unique study identification number. The database containing identification numbers and contact information will be stored separately from study data and will be used to link baseline, post-treatment, and 6-week follow-up assessments. This database will be stored on a password-protected computer accessible only to research staff and will be destroyed immediately upon completion of the study. Study computers will also be stored in a locked office accessible only to research staff (PI [name]'s laboratory space in the Department of Psychiatry). Identifying information (names and dates) will appear only on consent forms, payment receipts, and the contact

information form. All paper forms containing identifying information will be kept in a locked filing cabinet in [name]'s office (C201E) at the VA, separate from any data; and only research staff will have access to these filing cabinets. Audiotaped sessions, which will be used in fidelity coding, will not be labeled with identifying information and will be deleted permanently once fidelity coding is complete. Data collected using computer software will be stored electronically and identified by unique study number only. No personally identifying information will be included in the data. A password will be required to access data that are stored electronically, and only personnel involved with the project will have access to the electronic data. The computer-administered surveys provide an additional layer of confidentiality protection relative to paper and pencil surveys where staff would see a participant's data as they were entering or storing it.

Participants will be informed verbally and in writing during the consent process that mandatory reporting laws will be followed. Subjects who indicate danger to themselves or others will be escorted to the emergency room.

Given the sensitive nature of information being collected, all data will be protected by a Certificate of Confidentiality and identified using unique ID numbers assigned to participants specifically for this project. Names and identifying information required for follow-up reminders will always be kept separate from research data and will not be used as study data. Computerized survey data will be stored electronically on the secure VA server. Digital audio recordings of sessions, which will be used to determine treatment fidelity, will be stored on password-protected computers to which only project staff will have access. All research staff will be trained in procedures for maintaining data and participant confidentiality. Study personnel will no longer have access to the study data when they are no longer part of the research team. Data will not be removed from the VA.

*Protocol modifications for individuals with a history of mania or bipolar disorder.* Because the sleep restriction component of CBT-I places individuals with a history of mania at risk for additional manic episodes, the treatment will be modified for these individuals (see Section 4 above) and individuals with a recent (past year) history of mania will be excluded.

*Data safety and monitoring plan.* PI [name] will monitor procedures to ensure that they conform to the approved protocol. Specifically, she will monitor (a) the progress of the research, including participant recruitment and retention and assessments of data quality; (b) adverse events and procedures for making determinations that there may be a change to the benefit-to-risk ratio of research participation; and (c) procedures to protect participant privacy and confidentiality. She will monitor all serious, unexpected, and other adverse or potentially adverse events. Serious adverse events include those resulting in death, inpatient hospitalization, a threat to life, persistent or significant disability or incapacity, congenital anomalies/birth defects, or serious health risk. Unexpected adverse events are those that were unforeseen based on the anticipated potential risks outlined in the study protocol and informed consent. Other adverse or potentially adverse events include those that may be causally related to study participation and lead to participant distress or drop-out.

PI [name] will monitor data quality and adverse events on an ongoing basis. All serious and unexpected adverse events will be reported to the IRB within 24 hours of receipt of information. Other adverse or potentially adverse events will be monitored and reported at annual continuing reviews.

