**Baseline assessment.** Participants will provide written informed consent prior to completion of baseline (see Table 1). In the case of remote baseline assessments, an RA will walk the participant through an electronic version of the written consent form, which they will be asked to sign electronically via the Qualtrics platform. The RA will then print and sign the electronic version of the participant's consent. The baseline evaluation will involve assessment of substance use and sleep disorders and full eligibility criteria using the Mini International Neuropsychiatric Interview (MINI) 7.0.2. Consistent with standard practice, those who endorse symptoms of sleep-related breathing disorders, restless legs syndrome, periodic limb movement disorder, or narcolepsy will be referred for polysomnography. Given the prevalence of sleep apnea in this population, individuals who meet all eligibility criteria but report symptoms of sleep apnea will complete one night of holter monitoring (using an Evo Holter Recorder, SpaceLabs Healthcare) at home in their own beds to rule out for sleep apnea.

Eligible participants will complete baseline assessment measures and will be randomly assigned to either the CBT-I or SH condition. Participants in both conditions will be oriented to the prospective sleep diary, which

they will be asked to complete every morning for the next 6 weeks. The RA will provide all participants with a general handout on sleep hygiene (from the National Sleep Foundation website) and answer any questions they may have about the guidelines.

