Use	Construct	Measure(s)	BL	Post	6wk
Cov	Demographics	See instruments	X		
	Other drug use , past 6 weeks	Drug Use Screening Inventory	X	X	X
	Use of sleep medication	Daily Sleep Diary (Carney et al., 2012)	X	X	X
Aim 1	Recruitment	Completion of ≥ 1 session of CBT-I		X	
	Retention	Completion of 6/6 sessions of CBT-I		X	
	Treatment satisfaction , measured separately for CBT-I and CBT-AUD	Client Satisfaction Questionnaire (Larsen et al., 1979)			X
Aim 2	% abstinent days , past 6 weeks	Timeline Follow-back (TLFB) for alcohol (Sobell & Sobell, 1996)	X	X	X
	% heavy-drinking days (≥4/5 drinks/day for women/men)				
	Alcohol problems , past 6 weeks	Short Inventory of Problems ([name] et al., 1995)	X	X	X
	Use of alcohol or other drugs to help with sleep , past 6 weeks	Daily Sleep Diary (Carney et al., 2012)	X	X	X
	Insomnia severity , past 2 weeks	Insomnia Severity Index (Morin et al., 2011)	X	X	X
	Total wake time , average past week	Daily Sleep Diary (Carney et al., 2012)	X	X	X
	Sleep quality , average past week	Daily Sleep Diary (Carney et al., 2012)	X	X	X
	Dysfunctional beliefs, past month	Dysfunctional Beliefs about Sleep Scale	X	X	X
Aim 3	Treatment-related learning	Project SAVE Alcohol Quiz Project SAVE Alcohol Vignette	X	X	X
	Executive functioning	Psychomotor Vigilance Task (Dinges et al., 1985) N-back Task (Schmiedek et al., 2014) Monetary Choice Questionnaire UPPS Measure of Impulsivity Cognitive Failures Questionnaire	X	X	X
	Negative affect , past week	Positive and Negative Affect Schedule	X	X	X
	Emotion regulation , past 30 days	Brief Difficulties in Emotion Regulation Scale (Bjureberg et al., 2016)	X	X	X
	Alcohol craving , past week	Penn Alcohol Craving Scale	X	X	X
	Mental health symptoms	PTSD Checklist for DSM-5 Patient Health Questionnaire-9 for depression GAD-7 measure of anxiety Satisfaction with Life Scale	X	X	X

*Note.* BL=baseline. Cov = potential covariates. Post = post treatment. Wk = week.

*Blinding.* PI [name] will not be blinded to block size or participant assignment because she will inform study therapists of participant assignment to conditions. However, PI [name] and study therapists will be blinded to assessment outcomes, and the assessment RA will be blinded to participant condition.

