## **5. Inclusion/Exclusion Criteria**

Eligibility criteria include (a) participation in the Addictions Treatment Program at the Truman VA, (b) DSM-5 criteria for moderate to severe Alcohol Use Disorder, (c) alcohol use in the past 2 months at baseline, and (d) the DSM-5 episodic criterion (duration at least 1 month) for Insomnia Disorder.

Participants will be excluded if they are unable to provide informed consent, demonstrate cognitive impairment (Mini Mental Status Exam score <26), report a manic episode or seizure in the past year (contraindications for CBT-I), have a severe psychiatric disorder that requires immediate clinical attention (e.g., psychosis, suicidal ideation with intent and plan), or began a sleep medication in the past 6 weeks. Consistent with standard practice, those who endorse symptoms of sleep-related breathing disorders ( $\geq 2/8$  symptoms on the STOP-BANG), restless leg syndrome, periodic limb movement disorder, or narcolepsy will be referred for polysomnography.

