*Early stopping rules.* PI [name] will monitor adherence to the study protocol and adverse events on an ongoing basis and discuss these issues with the research team during weekly meetings. All serious and unexpected adverse events will be reported to the IRB within 24 hours of receipt of information. Other adverse or potentially adverse events will be monitored and reported at annual continuing reviews. After discussion with the IRB, we will discontinue the trial if there is (a) compelling evidence from this or another study of a serious adverse effect of CBT-I that has potential to override potential benefit, (b) compelling evidence from this or another study of a significant beneficial effect of CBT-I, such that continued denial to other groups would be unethical, or (c) low probability of addressing study aims within a feasible time frame.

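### New manic episodes are a named risk of sleep restriction, but no scheduled measure asks about them after baseline, and a foreseen episode that is not serious can reach the IRB only at annual review

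*Combined protocol and SAP*

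**What the plan says.** **The hazard.** Section 8 (Risks) gives the reason for special handling: "Because the sleep restriction component of CBT-I places individuals with a history of mania at risk for additional manic episodes". It goes on: "There are no other known iatrogenic effects of CBT-I or completion of sleep diaries". The word *other* shows that the protocol counts the hazards it has just listed as known.

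**Who is kept out.** Section 5 excludes people who "report a manic episode or seizure in the past year (contraindications for CBT-I"). Section 4 and the paragraph on mania in Section 8 use the same one-year window. That paragraph says therapy will be adapted for people with a history and cites Section 4 for the details.

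**What is measured.** Section 4 (Baseline assessment) describes assessing "full eligibility criteria using the Mini International Neuropsychiatric Interview (MINI) 7.0.2". The mental health row of Table 2, marked for baseline, post-treatment and 6 weeks, lists "PTSD Checklist for DSM-5 Patient Health Questionnaire-9 for depression GAD-7 measure of anxiety Satisfaction with Life Scale".

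**What is reported, and when.** Sections 7 and 8 send serious and unexpected events to the IRB within 24 hours. Section 8 defines the second class: "Unexpected adverse events are those that were unforeseen based on the anticipated potential risks outlined in the study protocol and informed consent". For everything else, "Other adverse or potentially adverse events will be monitored and reported at annual continuing reviews".

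**The concern.** The protocol identifies a specific psychiatric harm, admits some of the people it says are at risk, and then schedules nothing after baseline to find out whether the harm occurred. Its reporting rules also work against early notice: once a harm has been written into the risk section it no longer counts as unexpected, so it loses one of the two routes to prompt IRB review.

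Two things are at stake. One is participant safety, because the IRB could learn late of an episode that the protocol itself anticipated. The other is how the adverse-event record can be read. If episodes come to light mainly through conversation with a study therapist, CBT-I has far more opportunity to produce a report than sleep hygiene, and a count by arm would mix true occurrence with opportunity to be noticed.

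**Working it through.** The plan states no figure on this point, so the check sets the sections against each other.

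1. **Exposure.** Section 8 ties the risk to a history of mania. Sections 4, 5 and 8 exclude only episodes in the past year. People whose last episode is older are therefore eligible, and Section 8 confirms this by promising them adapted therapy. Section 4 mentions mania only as a past-year exclusion. Its account of CBT-I describes one course, with weekly titration of time in bed, and no variant for these participants.

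2. **Scheduled ascertainment.** The MINI is described once, at baseline, for eligibility. The measures Table 2 repeats after baseline cover drug use, drinking, sleep, beliefs about sleep, treatment-related learning, executive function and impulsivity, affect, emotion regulation, craving, PTSD, depression, anxiety and life satisfaction. None is a mania or hypomania measure. Neither of the two post-baseline visits includes one, in either arm.

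3. **Unscheduled ascertainment.** Section 7 has the PI monitor adverse events continuously and discuss them weekly with the team, but no method of eliciting them is given. CBT-I participants have five weekly individual sessions and possibly a sixth. Sleep hygiene participants receive a one-page handout. Section 4 (Blinding) also blinds the PI and therapists to assessment outcomes, and no route is described by which the assessment RA would pass on a mood change noticed at a visit.

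4. **Classification.** Take a manic episode after randomisation that does not lead to hospital admission and apply Section 8 in order:
   - *Serious?* Yes, if it threatens life, causes significant disability or incapacity, or amounts to a serious health risk. It then has the 24-hour route. Suppose it does none of these.
   - *Unexpected?* No, because Section 8 foresees it.
   - *Other?* Yes, if it may be related to participation and leads to distress or drop-out. It is then reported at annual review.
   - *None of these?* If it causes neither distress nor drop-out, no described class clearly captures it.

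5. **Consequence for timing.** For the same event, the IRB interval is 24 hours if the protocol had not foreseen it, and up to the time of the next annual review because it did.

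**The case against.** **The promised adaptation may remove the risk.** It might reduce it, but Section 4 does not describe it, so the residual risk cannot be judged. An adaptation would in any case not measure whether episodes occur.

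**Someone would notice.** Much of this stands. Adverse events are reviewed continuously, CBT-I therapists meet participants weekly, sessions are recorded with permission and reviewed by licensed psychologists, and both arms are in an addictions programme. A reader might infer that nobody would be looking, or that an episode would certainly go unrecorded. The documents do not support that. What is missing is a structured question put equally to both arms. Also, the description of *other* events is introduced by *include*, so it is not exhaustive, and failure to record is only a possibility.

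**The seriousness list is wider than hospital admission.** This is correct. Some episodes outside hospital would go to the IRB within 24 hours. The gap concerns only those meeting none of the criteria. One could also read *serious and unexpected* as requiring both conditions, so that even a hospitalised episode would escape the fast route. Section 8 defines the two classes separately, which favours the narrower reading used here.

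**The stopping rule is unaffected.** A reader might infer that the first rule in Section 7 cannot operate. It accepts "compelling evidence from this or another study of a serious adverse effect of CBT-I that has potential to override potential benefit", so it does not depend solely on this trial's monitoring, and no change to it is justified.

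**No safety conclusion is planned.** This is also correct. The statement that risks are minimal is made in advance, and the aims are feasibility, acceptability and initial efficacy. The trial is not set up to claim that the treatment is safe.

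**Post-treatment is late.** The first repeat visit follows the five core sessions, so the added questions would not protect a participant during them as well as prompt reporting would. This limits the benefit of the questions. It does not affect the reporting change.

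**Conclusion.** The point holds in a limited form. A harm named in the protocol has no scheduled measure after baseline, opportunities for detection differ by arm, and an episode that is foreseen and not serious can reach the IRB only at annual review. The PI may know of it much sooner; the delay is to the IRB.

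No numerical size can be given. It is tempting to compute an upper confidence bound from zero events among all CBT-I participants, but the protocol names the risk only for those with a history of mania. The documents do not say how many of these there would be, or what share of episodes would surface unprompted.

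The conclusion assumes that some participants have a history older than one year, that Table 2 is the complete assessment schedule, and that serious and unexpected events each trigger the 24-hour rule. The definition of *unexpected* also refers to the consent form, which was not available, so whether it names mania could not be checked.

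**What to change.** 1. **Table 2.** Have the blinded assessment RA repeat the baseline MINI mania and hypomania items at post-treatment and at 6 weeks, in both arms, worded to cover the time since the last visit. Any positive answer goes to the PI as an adverse event. Say so in the Blinding paragraph, since the PI is otherwise blind to assessment outcomes.
2. **Section 8, data safety and monitoring plan.** State that a manic or hypomanic episode after randomisation is recorded as an adverse event whether or not it causes distress or drop-out. State its IRB reporting time explicitly, so that being foreseen does not by itself move it to annual review. Align the matching sentences in Section 7.
3. **Reporting.** List episodes descriptively by arm and by baseline history of mania, with no test. The subgroup may be very small.
4. **Sections 4 and 8.** Reconcile the reference to adapted therapy with the text it points to. What the adaptation is, and the clinical response to an episode, are for the sponsor to set.

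The cost is a few interview items at two existing visits, short additions to the reporting and blinding text, and one descriptive table. Visits become slightly longer and there may be a few more reports. No new visit, staff or committee is needed.

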Participants will also receive reminder texts/calls, have access to free parking, and receive treatment at no cost.

*Cognitive Behavioral Therapy for Insomnia (CBT-I).* CBT-I will be delivered individually, in person, in five weekly one-hour sessions. A sixth week of treatment will be included – and scheduled for the same date as the post-treatment assessment – if the participant and research team agree that it would be beneficial (e.g., if a participant has difficulty grasping cognitive therapy concepts). Study therapists will follow the 2014 CBT-I in Veterans manual developed by leading researchers in the behavioral sleep medicine field (see Table 3). Intervention components include (1) sleep hygiene: limiting naps; avoiding caffeine, tobacco, alcohol, and rich/heavy foods before bedtime; exercising; establishing a bedtime routine; and creating a comfortable sleep

Table 1. *Assessment, therapy, and payment schedule*

Week	Assmt	CBT-I	Paymt	Bonus
1	BL		10	
2		S1	20	10
3		S2		
4		S3		
5		S4		
6		S5		
7	Post-tx	(S6)	40	
8				10
9				
10				
11				
12	1mo		50	
13				10

*Note.* 1mo = 1 month. Assmt = assessment. BL = baseline. Bonus = bonus payment for completion of all 7 daily surveys. Paymt = standard payment. Tx = treatment.

environment; (2) sleep restriction: limiting time in bed in order to improve sleep efficiency, or the percentage of time in bed that is actually spent sleeping; time in bed will be titrated each week based on sleep efficiency; (3) stimulus control: strengthening association between bedroom and sleep to decrease conditioned arousal; (4) relaxation: diaphragmatic breathing, progressive muscle relaxation, and visual imagery to reduce arousal; and (5) cognitive therapy: identifying and challenging thoughts that interfere with sleep.

*Sleep hygiene (SH).* All participants will receive a one-page handout on sleep hygiene. This is the only intervention that participants assigned to the SH condition will receive and is consistent with what may be expected as standard care in a doctor's visit with a primary care physician.

Table 2. Survey Instruments and Schedule of Administration

Use	Construct	Measure(s)	Cut-score		
Use	Construct	Measure(s)	BL	Post	6wk
Screen	Insomnia severity , past 2 weeks	Insomnia Severity Index (Morin et al., 2011)		≤ 9 excluded at phone screen	
	Sleep apnea , past month	STOP questionnaire (Chung et al., 2008)		≥ 3 excluded at phone screen	

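### Early non-serious fatigue need not be recorded as an adverse event, and counts of non-serious events would not be comparable between CBT-I and SH

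*Combined protocol and SAP*

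**What the plan says.** **The predicted risk.** Section 8 lists the risks of taking part, the last being loss of confidentiality: "Potential risks include: temporary daytime fatigue (due to restriction of time in bed), subjective discomfort from answering questionnaires, coercion, and the possibility of a breach". Fatigue is the only physical item in that list. Participants are to be told that "restricting their time in bed may increase daytime fatigue for the first few weeks of treatment", and that it should pass as time in bed is expanded.

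**The event classes (Section 8, data safety and monitoring plan).**
- Serious, defined by outcome: "Serious adverse events include those resulting in death, inpatient hospitalization, a threat to life, persistent or significant disability or incapacity", with birth defects and serious health risk also listed.
- Unexpected: "Unexpected adverse events are those that were unforeseen based on the anticipated potential risks outlined in the study protocol and informed consent".
- Other: "Other adverse or potentially adverse events include those that may be causally related to study participation and lead to participant distress or drop-out".

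Serious and unexpected events go to the IRB within 24 hours. For the rest, "Other adverse or potentially adverse events will be monitored and reported at annual continuing reviews". No adverse-event form, question or elicitation schedule is described. The PI monitors events and, under Blinding in Section 4, knows the assignments.

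**Contact.** Section 4 and Table 1 give CBT-I five weekly sessions in weeks 2 to 6, with an optional sixth on the date of the post-treatment assessment. Of the sleep hygiene handout, Section 4 says: "This is the only intervention that participants assigned to the SH condition will receive". Both arms are assessed at baseline, post-treatment and follow-up (weeks 1, 7 and 12 in Table 1), keep diaries with reminders for missed entries, and attend usual alcohol treatment.

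**The concern.** A safety definition should at least capture the harm that the protocol itself predicts. Here an anticipated, non-serious event counts only if it passes two conditions together: possible relation to participation, and distress or drop-out. Fatigue that is marked but tolerated can fail the second condition and leave no trace. If few fatigue events are then reported, a reader cannot tell whether fatigue was rare or simply not recorded.

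The arms also differ in how often study staff see participants during the weeks when fatigue is expected. With no stated way of asking, reporting depends largely on what participants volunteer, and one arm has more occasions to do so. Judging possible relatedness falls within the remit of a PI who knows the assignments.

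At stake is the tolerability evidence that a feasibility and acceptability pilot should pass on to a later trial, together with the PI's commitment in Section 8 to watch for a change in the benefit-to-risk ratio.

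**Working it through.** The plan gives no safety figure, so there is none to reproduce. The check sorts the predicted event into the classes, compares timing, counts contacts, and shows how an illustration behaves.

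**1. Sorting early, non-serious daytime fatigue into the classes**

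| Class | Criterion | Fatigue without distress or drop-out | Fatigue with distress or drop-out |
|---|---|---|---|
| Serious | severe outcome | no | no, unless the outcome is severe |
| Unexpected | not foreseen in protocol or consent | no, it is named in both | no |
| Other | possibly related, and distress or drop-out | no | yes, if possibly related |

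The condition that excludes tolerated fatigue is distress or drop-out. Relatedness would not exclude it, since fatigue from sleep restriction is plainly possibly related.

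**2. Timing**
- Expected fatigue: first few weeks of treatment, which starts in week 2.
- Table 2 instruments, including the vigilance task: weeks 1, 7 and 12.
- Diary content listed in Section 4: night-time sleep variables, sleep medication, and alcohol or drug use for sleep. No daytime fatigue item is listed.

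So nothing listed for weeks 2 to 6 asks about daytime fatigue or events.

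**3. Scheduled study contacts (Table 1)**
- Weeks 2 to 6: CBT-I 5, SH 0.
- All post-baseline: CBT-I 5 + 2 = 7, SH 2.

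The optional sixth session falls on an assessment date and adds no separate occasion. Diary reminders and alcohol treatment are left out because they are common to both arms.

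**4. Illustration of direction, on assumed inputs**

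Suppose an event is equally common in both arms and persists, and each of k contacts gives an independent chance p that it is reported. The share recorded is 1 − (1 − p)^k. The documents give no value of p.

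| p (assumed) | CBT-I, k = 7 | SH, k = 2 | Ratio |
|---|---|---|---|
| 0.1 | 1 − 0.9^7 = 52% | 1 − 0.9^2 = 19% | 2.75 |
| 0.2 | 79% | 36% | 2.2 |
| 0.3 | 92% | 51% | 1.8 |
| 0.5 | 99% | 75% | 1.3 |

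For an event spanning three sessions and gone by week 7, with no question about the past, the CBT-I share is 1 − (1 − p)^3, or 27% at p = 0.1 and 88% at p = 0.5. The SH share is 0%. These figures restate their assumptions: they show which way unequal contact pushes the counts, not by how much in this trial.

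**The case against.** Several stronger conclusions are tempting, and the case against them is good.

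- **A reader might infer that stopping rule (a) is undermined.** It turns on "compelling evidence from this or another study of a serious adverse effect of CBT-I". Serious events are defined by outcome, with no relatedness or distress condition, and the rule also admits outside evidence. Unrecorded mild fatigue does not feed it.
- **A reader might infer that the relatedness condition distorts all safety counts.** It applies only to *other* events. The text also does not say that relatedness is judged before an event is recorded.
- **A reader might infer that almost nothing in SH can qualify.** The test is relation to study participation, not to CBT-I. Questionnaire discomfort, coercion and breach of confidentiality can arise in either arm.
- **A reader might infer that a near-miss accident fits no class.** It is not among the named risks, so it could be unexpected, or a serious health risk.
- **A reader might take a ratio such as 2.75 as the expected bias.** No reporting rate is documented, and the plan does not say that therapists elicit events. Differential capture is an inference.
- **A reader might infer that a planned analysis is invalid.** Section 7 plans no between-arm safety comparison, and the minimal-risk statement is a belief held in advance.

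It is also fair that *include* leaves the *other* class open, that Table 2 names instruments without their items, and that the protocol has safeguards: ongoing PI monitoring, weekly team review, a floor on time in bed, and advice on fatigue.

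What survives is narrower. No criterion beyond distress or drop-out is given for an anticipated non-serious event, no method of asking is described, and the safeguards record nothing about fatigue during the weeks when it is expected.

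**Conclusion.** The point holds in limited form. Under the stated definitions, non-serious daytime fatigue that causes neither distress nor drop-out need not be recorded, and no measure listed for weeks 2 to 6 would pick it up. With five study sessions against none in that window, counts of non-serious events would be incomplete and not comparable between arms. Serious and unexpected events are exposed only to unequal ascertainment.

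This rests on reading the definition as written, on the content listed for the diary and Table 2, and on the inference that more study contact gives more opportunity to report. The documents do not allow the bias to be sized. No prespecified analysis is damaged; the loss falls on later arm comparisons and on any benefit-risk judgement drawn from the pilot. It is a low-cost improvement worth making.

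**What to change.** 1. **Definition.** Redefine *other adverse events* as any new or worsened event in either arm, recorded regardless of cause, with relatedness assigned after recording.
2. **Same question in both arms.** At post-treatment and 6-week follow-up, use one scripted or self-completed adverse-event question covering the whole period since the last assessment. Give it after the outcome measures, by form or through someone other than the blinded RA: an answer that mentions restricted time in bed would reveal the assignment before the 6-week outcomes are collected. Someone other than that RA should read the forms promptly, because serious and unexpected events carry a 24-hour reporting duty.
3. **Diary.** First reconcile the schedule. The baseline paragraph of Section 4 asks for an entry every morning for 6 weeks. Table 1 pays diary bonuses in weeks 2, 8 and 13, and Section 8 speaks of three complete weeks. If diaries do run in both arms through weeks 2 to 6, add one daytime fatigue or sleepiness item. If they do not, the item would miss most of the window, and recall at post-treatment would be the only source common to both arms.
4. **Reporting.** Tabulate events by arm, descriptively, from these equal-contact sources, and list events volunteered to therapists separately.

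**Cost.** A revised definition, a short form at two existing visits and possibly one diary item. More minor events will be logged, participant burden rises slightly, and a small unblinding risk remains, which the ordering in item 2 limits. No new visits are needed and no treatment rule changes.
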